1.6 Study Variables

A. Independent Variables, Interventions, or Predictor Variables

Independent variable will be whether the patient received a nasal swab with Povidone-Iodine or sterile saline.

B. Dependent Variables or Outcome Measures

The decrease in CFUs in multiple time spans after intervention.

1.7 Drugs/Devices/Biologics

A. Schedule and Administration

Povidone-lodine 10% solution will be given intranasally as a swab with two swabs/nostril for patients in the experimental arm of the study. The control arm will be given sterile saline via the same method.

B. Drug/Device Accountability and Storage Methods

The study drugs will be dispensed by the pharmacy. The study drugs will be administered by study investigators.

1.8 Specimen Collection

A. Primary Specimen Collection

- **Types of Specimens**: 4 sets of nasal mucosal samples per subject to be collected by a investigator at preoperative, intraoperative, and postoperative intervals.

 A study participant number will be associated with each sample.
- Transport: All cultures will be sent to an outside lab for testing per the following protocol. All swabs will be placed in a 15 mL conical screw-top tubes containing sterile Phosphate Buffered Saline (PBS) solution. The samples will then be shipped the same day by 3 PM in a foam-insulated cooler with ice packs via overnight delivery to the testing facility.
- Processing: Swabs will be analyzed and enumerated by an outside testing facility for the presence of *S. aureus*, MRSA, and *S. epidermidis*.
- **Storage**: The specimens will be stored in the cooler described above and will be shipped out to the lab that same day. Prior to shipping, they will only be accessed by the study team.
- Disposition: Samples will be discarded after the lab has analyzed them.

B. Secondary Specimen Collection

■ N/A

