1.3 Research Design and Methods

Implement povidone-iodine (10%) pre-operative nasal decolonization for patients undergoing same-day surgery and evaluate efficacy and tolerability of this intervention in eradicating nasal colonization.

HRP-503a - TEMPLATE - Interventional Research Protocol 1.1.21 Protocol Title: Povidone-lodine for nasal decolonization

A. Research Procedures

This will be a prospective single-blinded randomized placebo-controlled trial of two applications of a nasal 10% PI solution used on the intranasal mucosal surfaces of each nostril in the preoperative holding area within 2 hours prior to surgical incision compared with sterile saline using the same technique. Both the PI and sterile saline will be applied by rotating the swab over the intranasal mucosal surface for 15 seconds; this process will be performed twice for both nostrils, using a new swab for each of the 4 applications. 200 subjects will be chosen from a pool of patients arriving at University Hospital, Newark, NJ for outpatient surgery. Inclusion criteria include community-based patients ages 18-80, ASA 1-3 who will be undergoing an outpatient surgery scheduled for at least 1 hour and up to 6 hours duration. Exclusion criteria include pregnancy, allergy to povidone-iodine, infectious indication for surgery or preexisting known infection/wound, known immunocompromised state, use of antibiotics, chemotherapy, or steroids within 1 month prior to surgery. Additionally, patients presenting for surgeries where field avoidance prevents intraoperative access to the nares (e.g., ENT/OMFS/ophthalmology procedures) will be excluded. Patients will be randomly divided into two groups: control (sterile saline) vs. experimental (PI) This will be done via simple randomization using a computer program that assigns patients as they present into either the control or experimental group while maintaining an overall approximately even ratio of subjects in each group.

B. Data Points

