Potential subjects will be identified from surgical schedule. Patients will be asked for informed consent in the same-day surgery (SDS) unit. They will be given sufficient time to read the IC document and ask questions. While in the preoperative holding area, patients will be asked to sit upright at a 45-90° angle to prevent drainage into the nasopharynx. All patients will first be swabbed for a nasal swab specimen, once in each nostril. Patients will then receive the appropriate nasal applications depending on the group into which they were sorted: Povidone-Iodine or saline. The tolerability assessment of investigating drug will be done with every subject at the Pre-operating room and PACU by a few criteria as burning/itching, pain, irritation, epistaxis, runny nose, and others. Nasal swab specimen will be obtained by the anesthesiologist intraoperatively 1, 2 and 3 hours after investigational drug application as studies have shown that there a significant decrease in colony-forming units of MRSA even within 1-hour post-treatment [9, 10]. These cultures may be intraoperative or postoperative depending on the length of surgery. There will also be a nasal swab specimen obtained while the patient is in the PACU. Study subjects will be stratified according to age, sex, comorbidities, and ethnicity. Additionally, the type of surgery, duration of surgery (Incision start to incision close), number of surgeons present during the procedure (Include all individuals scrubbed in), postoperative hospital stay length, and intraoperative time (patient in OR to patient out OR) will be used in data analysis. The purpose is to identify variables that increase the incidence of surgical site infection.

C. Study Duration

The study will take approximately 2 years, but chart review may continue up to 4 months after the last patient in the study has their procedure. Chart review of subject's postoperative surgical clinic visits will be performed up to 30 days to monitor for any surgical site infection.

D. Endpoints

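### Swabs travel overnight in plain PBS with no iodine neutraliser specified, so carry-over in povidone-iodine tubes could inflate the primary CFU decrease

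*Combined protocol and SAP*

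**What the plan says.** Section 1.8 (Specimen Collection) sets out how samples are handled and presents this as the procedure to follow: "All cultures will be sent to an outside lab for testing per the following protocol". The medium is given in one sentence: "All swabs will be placed in a 15 mL conical screw-top tubes containing sterile Phosphate Buffered Saline (PBS) solution". The tubes are then "shipped the same day by 3 PM in a foam-insulated cooler with ice packs via overnight delivery to the testing facility". On arrival, "Swabs will be analyzed and enumerated by an outside testing facility for the presence of" *S. aureus*, MRSA and *S. epidermidis*, and samples are discarded after analysis. The PBS fill volume is not given. No section mentions a neutraliser, a neutralising transport medium, a rinse or a carry-over control.

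The order of events is in section 1.3. Baseline comes before treatment: "All patients will first be swabbed for a nasal swab specimen, once in each nostril". Then "Both the PI and sterile saline will be applied by rotating the swab over the intranasal mucosal surface for 15 seconds", twice in each nostril. Follow-up sampling is from the same nose: "Nasal swab specimen will be obtained by the anesthesiologist intraoperatively 1, 2 and 3 hours after investigational drug application", with a further swab in the PACU. Section 1.7 confirms what the other arm receives: "The control arm will be given sterile saline via the same method".

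The primary endpoint (section 1.3 D) is the fall in *S. aureus*/MRSA CFU among patients positive at baseline. Sections 1.5 and 6.1 analyse it with paired t tests, a two-sample t test on the pre-to-post CFU difference, and a mixed regression over follow-up times.

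**The concern.** The test product is an antiseptic, and the outcome is the number of organisms still alive when the laboratory plates the swab the next day. If a follow-up swab picks up active iodine along with the bacteria, killing need not stop when the swab leaves the nose. It could continue in the tube until the iodine is neutralised or exhausted. Plain PBS is not described as neutralising anything.

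The usual protections do not help because the exposure is lopsided. Subtracting baseline removes nothing, since baseline tubes hold no study iodine. The saline arm is no control for it, since its tubes hold none either. The t tests and the mixed model take the counts as given. Once a sample is plated, organisms lost in the tube cannot be told apart from organisms killed in the nose, and discarded samples cannot be re-tested. What is at stake is whether the primary result measures decolonisation of the patient or partly killing in transit.

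**Working it through.** The plan gives no figure for carry-over or recovery, so there is none to reproduce. The sample size of 85 per group does not use the specimen handling.

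**Which tubes can hold study iodine** (sections 1.3, 1.7, 1.8)

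| Tube | PI arm | Saline arm |
|---|---|---|
| Baseline, before application | no | no |
| 1, 2, 3 hours and PACU, after application | possible | no |

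Only one of the four cells is exposed.

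**Effect on the endpoint.** Let *B* be the baseline count, *R* the true proportional decrease in the nose, and *f* the share of CFU on a PI-arm follow-up swab killed in the tube. No section gives *R* or *f*; both are assumed here.

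- True follow-up count: *B*(1 − *R*). Count at the laboratory: *B*(1 − *R*)(1 − *f*).
- Observed decrease: 1 − (1 − *R*)(1 − *f*).
- Excess over the truth: *f*(1 − *R*). With *f* = 1 this reaches its ceiling, 1 − *R*.
- Factor on the pre-to-post CFU difference, the plan's own scale: 1 + *f*(1 − *R*)/*R*.
- Between arms: if the saline arm falls by *S*, the observed contrast is *R* + *f*(1 − *R*) − *S* and the true contrast is *R* − *S*. *S* cancels, so the contrast grows by the same *f*(1 − *R*).

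| True *R* | *f* | Observed decrease | Excess (points) | Factor on CFU difference |
|---|---|---|---|---|
| 50% | 10% | 1 − 0.50 × 0.90 = 55% | +5 | 1.10 |
| 50% | 50% | 1 − 0.50 × 0.50 = 75% | +25 | 1.50 |
| 50% | 90% | 1 − 0.50 × 0.10 = 95% | +45 | 1.90 |
| 90% | 10% | 1 − 0.10 × 0.90 = 91% | +1 | 1.01 |
| 90% | 50% | 1 − 0.10 × 0.50 = 95% | +5 | 1.06 |
| 90% | 90% | 1 − 0.10 × 0.10 = 99% | +9 | 1.10 |

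The ceiling is +50 points when the true decrease is 50% and +10 when it is 90%.

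**Why ordinary die-off in PBS is different.** Suppose a share *g* dies in every tube regardless of arm. Baseline becomes *B*(1 − *g*) and follow-up *B*(1 − *R*)(1 − *g*). The proportional decrease is still *R*, and the absolute difference shrinks by the same factor in both arms. Such die-off does not favour PI; iodine carry-over does.

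The table uses one *f* for all follow-up tubes. The formula also works tube by tube: if residue fades with time, *f* and the excess are smaller at 3 hours than at 1 hour.

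**The case against.** The strongest reply is that the documents show an opportunity for carry-over, not that it happens. Three things are needed: active iodine on the mucosa 1 to 3 hours after application, enough of it transferred on a sampling swab, and continued killing after dilution in PBS on ice packs. No section supplies any of these. This stands: the size is unknown and may be nil, and the values of *f* above are no evidence that the problem is real.

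A second reply is that counting is delegated to an outside laboratory whose method is not in the protocol, so the tubes may already contain a neutraliser. This also stands, and it is why the first step is a question. It does not remove the point, because section 1.8 presents itself as the procedure and names PBS alone. Neutralising only on arrival would come too late for anything killed overnight.

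A third reply concerns the remedy. The protocol is version 5, dated 05.10.23, with a page date of 9/5/2024 and a planned duration of about 2 years, so enrolment may be well advanced. A switch would split an already small baseline-positive subset by medium, and a sensitivity analysis by medium may then say little. It is also fair that a new fill should not be taken on trust: without a recovery check, one untested medium replaces another. These are reasons to switch carefully and to value the check; they do not make plain PBS the safer choice.

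**Conclusion.** The concern holds. As written, the plan sends swabs from an iodine-treated nose overnight in PBS with no specified means of stopping the iodine. Only PI-arm follow-up tubes are exposed, so any resulting bias enlarges the apparent benefit of PI on the primary endpoint, and the planned analysis cannot remove it.

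The direction follows from the design. The size does not: it depends on residual iodine, swab pick-up, fill volume and killing on ice, none of which is given. Under the assumed *f* of 10% to 90%, the overstatement runs from 5 to 45 points for a true 50% decrease and from 1 to 9 points for a true 90% decrease. The conclusion also assumes that no neutraliser is present that the protocol fails to mention. This should be corrected because the primary endpoint is exposed and the remedy is cheap, not because a large bias has been shown.

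**What to change.** 1. Ask the laboratory what the tubes contain. If they already hold an iodine neutraliser, state it in section 1.8; nothing else need change.
2. If they do not, amend the transport paragraph of section 1.8, for example:

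> Every swab, in both arms and at every time point including baseline and PACU, goes into a tube of sterile PBS with an iodine neutraliser [name, concentration, fill volume].

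A named neutralising transport medium would serve equally well. The fill must be identical in all tubes, so that any effect of the neutraliser on recovery is shared by both arms and all times. It must be in the tube at collection.

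3. Preferably, have the laboratory run a recovery check. Use a PI load representative of mucosal residue at 1 to 3 hours rather than a freshly loaded swab; if that load is unknown, test a range and say so. Include an immediate-plating reference and set the acceptance limit beforehand.

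The cost is one question, a different tube fill and, if done, the laboratory check; patients undergo nothing extra. The real drawback is a change of measurement method if enrolment has begun. In that case, switch between patients and never within one, in both arms on the same date. Record the date, report a sensitivity analysis by medium, and list possible carry-over as a limitation for samples already processed.

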1.9 Data Collection

HRP-503a - TEMPLATE - Interventional Research Protocol 1.1.21 Protocol Title: Povidone-lodine for nasal decolonization

A. Primary Data Collection

[figure not shown]
- **Location**: Data collection will occur in the preoperative holding area, operating rooms, and post-anesthesia care unit of the University Hospital, Newark, NJ.
- **Process of Data Collection**: The investigator who is applying the saline or 10% PI to the study subjects will not be blinded. Nasal cultures will be obtained by the study team members. [name] will be overseeing the entire study.
- Timing and Frequency: There will be swab collections prior to the procedure, at the one-, two-, and three-hour marks after saline or 10% PI is administered.
- Procedures for Audio/Visual Recording: N/A
- Study Instruments: n/a
- Ethnographic Studies, Interviews, Or Observation: N/A
- Subject Identifiers: MRN only

B. Secondary Data Collection

N/A

1.10 Timetable/Schedule of Events

Figure 1 Timeline of study protocol

The study will last approximately 2 years from the beginning.

2.0 Project Management

2.1 Research Staff and Qualifications

[name] will be available all days of the study. Having worked in this hospital for many years, he is very knowledgeable about the study site, the culture, and the patient population. He will be enlisting the help of study assistants to aid in the collection of data and application of the nasal swabs but will be directly overseeing all of this to ensure everything is in order.

2.2 Research Staff Training

All involved study team members will be trained how to perform data collection and nasal swab application correctly.

2.3 Other Resources

N/a

HRP-503a - TEMPLATE - Interventional Research Protocol 1.1.21

Protocol Title: Povidone-Iodine for nasal decolonization

Protocol Version Date: v5 05.10.23

9/5/2024

3.0 Multi-Center Research

N/A

4.0 Subject Considerations

4.1 Subject Selection and Enrollment Considerations

A. Method to Identify Potential Subjects

Subjects will be chosen from a pool of patients arriving at University Hospital, Newark, NJ for outpatient surgery.

B. Recruitment Details

Subjects meeting the inclusion criteria will be identified by the anesthesiologist preoperatively and be given information about the study and what their participation entails. They will also be given a recruitment flyer with information and will have the opportunity to ask any questions they may have.

C. Subject Screening

- Inclusion Criteria
- community-based English or Spanish speaking patients ages 18-80
- · willing and able to consent
- American Society of Anesthesiology (ASA) 1-3
- undergoing an outpatient surgery for at least 1 hour and up to 6 hours duration

Exclusion Criteria:

- pregnancy
- allergy to povidone-iodine
- infectious indication for surgery or preexisting known infection/wound
- immunocompromised state
- use of chemotherapy or steroids within 30 days prior to surgery
- use of antimicrobial therapy within 30 days prior to surgery
- surgeries where field avoidance prevents intraoperative access to the nares

D. Privacy Protections

No information about the patients will be revealed to anyone except the study team and providers involved in the care of the patients.

4.2 Obtaining Identifiable Information About Non-Subjects

N/A

4.3 Number of Subjects

A. Total Number of Subjects

HRP-503a - TEMPLATE - Interventional Research Protocol 1.1.21

Protocol Title: Povidone-Iodine for nasal decolonization

Using a one-sided alpha of 0.05 and a beta of 80%, we calculated that we would need at least 85 patients in each group for a total of at least 170 patients.

B. Total Number of Subjects If Multicenter Study

N/A

C. Feasibility

Based on the volume of same-day surgical procedures at University Hospital, Newark, NJ and the wide inclusion criteria for this study, having 170 total patients for the study should be feasible.

4.4 Consent Procedures

A. Consent Process

Location of Consent Process

In the SDS unit of University Hospital.

Ongoing Consent

N/A

Individual Roles for Researchers Involved in Consent

The study team members will be obtaining the nasal swabs and will be informing the patient of the study and obtaining consent.

Consent Discussion Duration

Enough time will be spent discussing the study with the patient until all patient's questions and concerns have been addressed.

Coercion or Undue Influence

Patients will be told that they are not obligated to participate in the study and that their care will not be affected by their decision.

Subject Understanding

Key questions will be asked of the patient during the discussion to verify the patient's understanding of the study and their role within it.

Protecting Privacy

Only the patient and patient's guest in the SDS unit will be present during the discussion.

B. Waiver or Alteration of Consent Process

Waiver or Alteration Details

N/A

Destruction of Identifiers

N/A

Use of Deception/Concealment

N/A

C. Documentation of Consent

Documenting Consent

Individuals will be asked to sign the consent document.

Waiver of Documentation of Consent (i.e., will not obtain subject's signature)

N/A

4.5 Special Consent Populations

A. Enrolling Minors-Subjects Who Are Not Yet Adults

Parental Permission

N/A

Non-Parental Permission

N/A

Assent Process

HRP-503a - TEMPLATE - Interventional Research Protocol 1.1.21

Protocol Title: Povidone-Iodine for nasal decolonization

Protocol Version Date: v5 05.10.23

9/5/2024

Expiration Date:

N/A

Documentation of Assent

N/A

Reaching Age of Majority During Study

N/A

B. Enrolling Wards of the State

N/A

Research Outside of NJ Involving Minors

N/A

C. Enrolling Non-English-Speaking Subjects

Spanish speakers will be enrolled. The Spanish version of the Informed Consent Form will be provided for Spanish speakers. **Process for Non-English-Speaking Subjects**.

The study team will use the Language Line Translator service the University Hospital provides for Spanish-speaking study participants.

Short Form Consent for Non-English Speakers

N/A

D. Enrolling Adults Lacking Decision-Making Capacity (Surrogate Consent)

N/A

Assessing Adult Capacity to Consent

N/A

Selecting a Surrogate & Consent Process

N/A

Subject Assent

N/A

Selecting a Witness to the Surrogate Consent Process

N/A

Removing a Subject

Any patient who wishes to be removed from the study will be removed immediately. Completion of the study regimen is defined as 2 applications of sterile saline or PI preoperatively and at least one intraoperative culture obtained perioperatively after surgical incision.

E. Special Consent Considerations

N/A

4.6 Economic Burden and/or Compensation for Subjects

A. Expenses

N/A

B. Compensation/Incentives

N/A

C. Compensation Documentation

N/A

4.7 Risks of Harm/Potential for Benefits to Subjects

A. Description of Risks of Harm to Subjects

Reasonably Foreseeable Risks of Harm

Minimal risk of harm given only intervention is nasal swabs.

HRP-503a - TEMPLATE - Interventional Research Protocol 1.1.21

Protocol Title: Povidone-Iodine for nasal decolonization

Protocol Version Date: v5 05.10.23

9/5/2024

Expiration Date:

Risk of Harm from an Intervention on a Subject with an Existing Condition

N/A

Other Foreseeable Risks of Harm

N/A

Observation and Sensitive Information

B. Procedures which Risk Harm to Embryo, Fetus, and/or Pregnant Subjects

C. Risks of Harm to Non-Subjects

N/A

D. Assessment of Social Behavior Considerations

N/A.

E. Minimizing Risks of Harm

Care will be taken by the investigators to minimize any potential discomfort patients may feel from the nasal swabs. Electronic study subject data (demographic data, weight, height, medical history, diagnosis, surgery type, co-morbidities, concomitant medications, anesthesia/surgical record, surgical visit notes) will be obtained from the subjects' electronic medical record and stored on an excel file that is maintained on a password protected hard drive in a locked room in MSB E-546.

Certificate of Confidentiality

N/A

Provisions to Protect the Privacy Interests of Subjects

N/A

F. Potential Direct Benefits to Subjects

Patients in the experimental group may have a decreased risk of surgical site infection postoperatively.

5.0 Special Considerations

5.1 Health Insurance Portability and Accountability Act (HIPAA)

5.2 Family Educational Rights and Privacy Act (FERPA)

5.3 Code of Federal Regulations Title 45 Part 46 (Vulnerable Populations)

5.4 General Data Protection Regulation (GDPR)

5.5 NJ Access to Medical Research Act (Surrogate Consent)

N/A

6.0 Data Management Plan

6.1 Data Analysis

We expect a statistically significant decrease in S. aureus/MRSA colonization in cultures taken perioperatively after intervention in patients who received pretreatment with PI as compared to patients who received sterile saline. We assumed that S. aureus/MRSA suppression in 20% of patients would be clinically relevant and that up to 5% of patients may have suppression even without treatment. Using a one-sided alpha of 0.05 and a beta of 80%, we calculated that we would need at least 85 patients in each group for a total of at least 170 patients. A paired t-test will be used to compare preintervention

HRP-503a - TEMPLATE - Interventional Research Protocol 1.1.21

Protocol Title: Povidone-Iodine for nasal decolonization

Protocol Version Date: v5 05.10.23

9/5/2024

nasal culture CFUs to 1- hour postintervention, 2- hour postintervention, and 3-hour postintervention nasal culture CFUs. A 2-sample t test will be used to compare the difference in pre- and post-intervention CFUs between the control and experimental groups at any endpoint. Additionally, mixed regression analysis will be used to determine the effect of the intervention on the CFU counts over all follow-up time points.

The data will be stratified by type of surgery, duration of surgery, and number of surgeons present throughout the procedure. Additionally, the variables age, sex, race, comorbidities, postoperative hospital stay length, and intraoperative time will be used in data analysis. In addition, postoperative surgical site infection (SSI) surveillance for the study participants will be conducted at 7 and 30-day postop intervals.

An intent to treat analysis will include those who are enrolled in the study and meet eligibility requirements for the study. A per protocol analysis will include all eligible patients who complete the assigned study regimen. Completion of the study regimen is defined as 2 applications of sterile saline or PI preoperatively and at least two cultures obtained perioperatively.

